## INTRODUCTION

Shortening of the treatment time via accelerating orthodontic tooth movement (OTM) continues to be a relentless challenge and demand in the mainstream orthodontics. To date, several modalities have been investigated to accelerate OTM through mechanical, pharmacological, surgical and physical approaches.

Vibrating devices are another example of physical acceleration of OTM. AcceleDent vibrating device (OrthoAccel Technologies, Houston, Texas) has been introduced to the market in 2009. It was intended to be used by the patients in conjunction with fixed orthodontic appliances or aligners, for 20 minutes per day. It vibrates at a frequency of 30Hz and has a force amplitude of 20 grams. The mechanism of action is hypothesized to be via enhancing bone remodelling through increased RANKL expression together with elevation in IL-1 beta levels with a result in rise of the rate of tooth movement after application of vibration in humans

and mice, respectively. The results reported in the literature concerning the efficiency of these devices in acceleration of tooth movement are controversial.

The aim of this study was to investigate the effectiveness of AcceleDent Aura vibrating device on the rate of canine retraction. The null hypothesis was that there is no difference in the rate of canine retraction between AcceleDent Aura appliance group and no appliance group. Other side effects including pain and root resorption were also considered.

## **MATERIALS AND METHODS**

### **Trial Design**

This study was a parallel group two arm randomized controlled clinical trial with 1:1 allocation ratio that was reported following the CONSORT statement. The study was approved by the Evidence Based Center, and the Research Ethics Committee and performed at the Faculty of Dentistry, Cairo University, Egypt . All patients were acquainted with the study procedures, and signed informed consents. No changes or modifications were done to the original methodology of the research

after trial commencement. All methods were performed in accordance with the CONSORT guidelines and regulations.

### **Sample Size Calculation**

The sample size for the current study was calculated based on the results of Kau et al. A total sample size of 52 canines was calculated to detect a large effect size ( $d=0.8$ ) with 80% power and 5% significance level. This number has been increased to a total sample size of 64 canines to count for the expected sample attrition. The outcome variable is normally distributed. The sample size was calculated using G-Power program (University of Düsseldorf, Düsseldorf, Germany).

### **Participants, Eligibility Criteria, and Settings**

Subjects were selected according to pre-set eligibility criteria (Table 1) and randomly assigned to intervention (AcceleDent Aura) or no-appliance groups using computer randomization sequence generation (<https://www.random.org/>) with 1:1 allocation ratio. It was not possible to mask the patients or the orthodontist providing the treatment, however, the outcome assessor was masked to the intervention.

All subjects received pre-adjusted MBT 0.022x0.028-inch slot brackets (3M Gemini metal brackets, 3M Unitek Corporation, Monrovia, CA, USA) on their upper and lower arches excluding the upper first premolars. The upper arch wire sequence

in the initial levelling and alignment phase was tailored according to the severity of crowding from 0.014-inch NiTi archwire, until reaching 0.016x0.022-inch stainless steel arch wire. Self-drilling miniscrews (TADs-Habit, Korea), 1.8x8 mm were placed buccally perpendicular to the labial plate of bone at the mucogingival junction between the upper second premolar and first molar bilaterally. Indirect anchorage was prepared bilaterally by inserting a L-shaped 0.019x0.025-inch stainless-steel wire in the auxiliary tube of the upper first molar bands and fixed to the mini-screws with flowable composite.

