## ABSTRACT

**Objectives:** To investigate the effectiveness of AcceleDent Aura vibrating device on rate of canine retraction. **Materials and Methods:** Thirty-two patients requiring extraction of upper first premolars and canine retraction were randomly allocated with a 1:1 ratio into either no-appliance group or the AcceleDent Aura appliance group. Canine retraction was done applying 150gm of retraction force using NiTi coil springs on 16\*22 stainless steel archwires. The duration of the study was 4 months. Digital models were obtained directly after extraction of upper first premolars and at monthly intervals during canine retraction for recording the monthly as well as the total distance moved by the canine. Digitized models were superimposed on the initial model and data were statistically analyzed. Anchorage loss, rotation, tipping, torque and root condition were evaluated using cone beam computed tomography imaging. Pain was evaluated by visual analog scale. **Results:** No patients were dropped-out during this study. There was no statistically significant difference between both groups regarding the total distance travelled by the canine ( $P=0.436$ ), as well as the rate of canine retraction per month ( $P=0.17$ ). Regarding the pain level, there was no statistically significant difference between the two groups at day 0 ( $P=0.721$ ), after 24 hrs. ( $P=0.882$ ), after 72 hrs. ( $P=0.378$ ) and after 7 days ( $P=0.964$ ). **Conclusion:** AcceleDent Aura was not able to accelerate orthodontic tooth movement. Pain level couldn't be reduced by vibrational force

with an AcceleDent device during orthodontic treatment. Root condition was not affected by the vibrational forces.

**KEY WORDS:** AcceleDent; Acceleration of tooth movement; Vibrating devices; Canine retraction; Digital models

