## **Measurements used in the CBCT Analysis**

Measurements of the total distance of canine retraction, the canine tipping, torque and rotation were analysed by measuring the angles between the long axis lines for the canines and the three reference planes were measured to detect tipping and torque movements. Also, the angle between the horizontal line of the first molar and the sagittal plane to detect canine rotation.

For assessment of root resorption, the axial guided navigation method explained by Castro et al and Schwartz et al was used. Using the software In-vivo 5, version 5.3(Anatomage, Inc., Santa Clara, CA 95054, USA). the pre- & post-retraction CBCTs obtained for each patient were used to evaluate the effect of AcceleDent on root resorption, the linear length between the root apex and cusps tip was measured.

The evaluation was carried by two blinded examiners. In order to fully visualize the root, the CBCT image was re-oriented on each root so that the cross-section would pass through the long axis of each canine (Figure 5).

The degree of pain was measured by Visual Analog Score (VAS), these charts were filled by the patients for the following week after beginning of canine retraction at time intervals (0, 24 hours , 48 hours, 72 hours and 7 days ) and were gathered at the end of the week. The pain VAS was in the format of a chart that contained a series of 10-cm horizontal scales on which the patient marked the degree of pain (0 to 10, where 0 refer to no pain and 10 refer to sever pain) at the indicated time periods.

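### The pain conclusion goes beyond the design: unmasked self-report against no appliance, in the first week only, cannot show that vibration does not reduce pain

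*Combined protocol and SAP*

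**What the plan says.** - **Conclusion.** The Abstract states "Pain level couldn't be reduced by vibrational force". The rest of the sentence ties this to the AcceleDent device and to orthodontic treatment without a time limit.
- **Results behind it.** The Abstract gives four pain P values: 0.721 (day 0), 0.882 (24 hours), 0.378 (72 hours) and 0.964 (7 days). It gives no differences or confidence intervals.
- **Masking.** Participants, Eligibility Criteria, and Settings says: "It was not possible to mask the patients or the orthodontist providing the treatment, however, the outcome assessor was masked to the intervention". It does not say which outcomes the assessor masking covers. In Measurements used in the CBCT Analysis, "The evaluation was carried by two blinded examiners" stands just after the root resorption method.
- **Who scores pain, and when.** The same section says of the VAS that "these charts were filled by the patients for the following week after beginning of canine retraction". Scores are taken at 0, 24, 48 and 72 hours and at 7 days.
- **Comparator.** Subjects were "randomly assigned to intervention (AcceleDent Aura) or no-appliance groups". No sham or inactive device is described.
- **Status of pain.** The Introduction lists it among side effects: "Other side effects including pain and root resorption were also considered".
- **Analysis.** Statistical Analysis names tests for the rate of retraction and the total distance, but none for pain.

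**The concern.** The conclusion goes further than the design in three ways.

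1. **Agent.** It makes vibration the thing that failed. The arms also differ in wearing a device for 20 minutes a day, in keeping a daily usage chart (Interventions and Outcomes) and in knowing which group they were in. Without an inactive device, neither an effect nor its absence can be assigned to vibration alone.
2. **Time window.** It speaks of orthodontic treatment, but pain was charted for only one week.
3. **Certainty.** It turns non-significant tests into a statement that pain could not be reduced.

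A reader may then take the trial to have shown that vibration has no analgesic effect during treatment, which was not tested. The masking sentence adds to this: because it names no outcome, it can be read as covering pain, where the assessor is the unmasked patient.

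**Working it through.** **1. The plan's own figure.** Sample Size Calculation gives 52 canines for d = 0.8, 80% power and 5% significance; Statistical Analysis says tests are two-sided.
- Normal approximation: n per arm = 2(1.960 + 0.842)² / 0.8² = 24.5, so 25 per arm and 50 in total.
- Two-sample t-test (noncentral t): n = 25.52, so 26 per arm and 52 in total, with power 0.807. This matches the plan.
- Attrition: 52 / (1 − 0.1875) = 64, so the allowance is 18.75%.

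The figure is reproduced, but it counts canines. Pain belongs to the patient.

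**2. Precision for pain.** Inputs: 32 patients allocated 1:1 with no dropout (Abstract). Assumptions: 16 per arm, one score per patient per time point, and an independent t-test.
- Degrees of freedom = 2 × 16 − 2 = 30; critical t = 2.042.
- Noncentrality at d = 0.8: 0.8 × √(16/2) = 2.26, which gives power 0.59.
- Effect detectable with 80% power: d = 1.02.
- 95% CI half-width: 2.042 × √(2/16) = 0.72 SD.

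**3. What the four P values leave open.** Under the same assumptions, |d| = t(P) × √(2/16), and the approximate interval is |d| ± 0.72. The Abstract does not give the direction of the differences, so positive here means the direction of whatever difference was observed.

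| Time | P | \|d\| | Approximate 95% CI (SD) |
|---|---|---|---|
| Day 0 | 0.721 | 0.13 | −0.59 to 0.85 |
| 24 hours | 0.882 | 0.05 | −0.67 to 0.77 |
| 72 hours | 0.378 | 0.32 | −0.41 to 1.04 |
| 7 days | 0.964 | 0.02 | −0.71 to 0.74 |

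Whichever group had the lower scores, no interval excludes a reduction of 0.4 SD with the device. The data are compatible with no effect and also with a moderate one.

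**4. Time covered.** One week out of 16 (four four-week intervals) to about 17 (four calendar months) is 1/16 = 6.3% to 1/17 = 5.9%. This measures calendar coverage, not bias.

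**5. Masking set against measurement.** Patients were not masked, and patients completed the VAS. Assessor masking therefore cannot apply to pain. It can apply to measurements on models and images, but explicit blinding is stated only beside the root evaluation; the description of the model measurements in Interventions and Outcomes does not repeat it.

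**The case against.** **The limitation is disclosed.** The masking sentence itself says patients could not be masked, and the VAS is openly described as filled in by patients. This stands. A reader might infer that the plan claims a protection it lacked, but the documents never say that pain scores were masked. The fault is a statement without a stated scope.

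**The comparator fits the aim.** The Introduction asks about the effectiveness of the device, and its null hypothesis compares appliance with no appliance. The pain sentence also names the device. This stands too: a no-appliance control is a legitimate comparator and supports a statement about the device as provided. It does not rescue the wording that makes vibration the agent.

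**Lack of masking does not readily explain a null.** Expectation would usually favour the device and so create a false benefit. For illustration, with 16 per arm and no true effect, an assumed bias of 0.4 SD towards the device raises the chance of a significant result from 0.05 to 0.195. Only a bias against the device would hide a benefit: with a true benefit of 0.8 SD and an assumed opposing bias of 0.4 SD, power falls from 0.59 to 0.195. A reader might infer that discomfort from the device cancelled a real benefit, but the documents report neither such discomfort nor any expectation effect.

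**Pain is a side effect.** It has no power calculation of its own, and the retraction result does not depend on it. This limits the weight of the point but does not justify the wording of the conclusion.

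**Conclusion.** The point holds as one about the pain conclusion. The trial supports a statement that no difference in self-reported pain was detected between the device group and the no-appliance group in the first week of retraction, with patients aware of their group. It does not support assigning the absence of an effect to vibration, extending it to orthodontic treatment in general, or saying that pain could not be reduced.

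The size is about 59% power at d = 0.8 and a 95% CI half-width of about 0.72 SD. Both figures rest on 16 patients per arm, one score per patient per time point and a t-test; the documents confirm none of these for pain. The size and direction of any reporting bias cannot be derived.

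Two stronger readings are not supported: that the null pain result is false or was produced by lack of masking, and that a no-appliance control is unfit for the trial's aim. The canine retraction outcome is not affected by this point.

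**What to change.** 1. **Abstract, Conclusion.** Replace the pain sentence with: *No difference in self-reported pain was detected between the AcceleDent Aura and no-appliance groups in the first week of canine retraction; patients were not masked.*
2. **Pain results.** Report the between-group difference with its 95% confidence interval at each charted time, including 48 hours, for which the Abstract gives no P value. Name the pain test in Statistical Analysis.
3. **Participants, Eligibility Criteria, and Settings (minor clarification).** State that assessor masking does not apply to pain, which unmasked patients reported themselves. Have the sponsor confirm which model and CBCT measurements it covers, rather than assuming all of them.

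The cost is a narrower secondary conclusion and a little extra reporting from scores already collected. No new data, staff or device are needed.

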## **Cone beam Computed Tomography**

Pre- and post-retraction CBCT images were obtained for each patient using the same CBCT machine with the following parameters: Resolution (Voxel size): 0.3\0.3 mm, exposure time: 10-20 sec, Anode voltage: 57-90 kV, field of view (FOV): 6×8 cm limited to the maxilla, and anode current: 4-16 mA. A total of 36 CBCT images were obtained at the end of the study (18 pre-retraction and 18 post-retraction) upon which the analysis was done.

The DICOM files obtained from the imaging centre were manipulated using In vivo 5 (Anatomage) version 5.3 software to perform the CBCT measurements as follows: Landmarks (Table 2), reference lines/planes (Table 3) (Figure 4) and measurements (Table 4) were all recorded in their corresponding modules. Then, an analysis was created and saved to be used for all pre- & post-retraction CBCT images.

## **Measurements used in the CBCT Analysis**

Measurements of the total distance of canine retraction, the canine tipping, torque and rotation were analysed by measuring the angles between the long axis lines for the canines and the three reference planes were measured to detect tipping and torque movements. Also, the angle between the horizontal line of the first molar and the sagittal plane to detect canine rotation.

For assessment of root resorption, the axial guided navigation method explained by Castro et al and Schwartz et al was used. Using the software In-vivo 5, version 5.3(Anatomage, Inc., Santa Clara, CA 95054, USA). the pre- & post-retraction CBCTs obtained for each patient were used to evaluate the effect of AcceleDent on root resorption, the linear length between the root apex and cusps tip was measured.

The evaluation was carried by two blinded examiners. In order to fully visualize the root, the CBCT image was re-oriented on each root so that the cross-section would pass through the long axis of each canine (Figure 5).

The degree of pain was measured by Visual Analog Score (VAS), these charts were filled by the patients for the following week after beginning of canine retraction at time intervals (0, 24 hours , 48 hours, 72 hours and 7 days ) and were gathered at the end of the week. The pain VAS was in the format of a chart that contained a series of 10-cm horizontal scales on which the patient marked the degree of pain (0 to 10, where 0 refer to no pain and 10 refer to sever pain) at the indicated time periods.

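### The only angle stated for canine rotation is taken on the first molar, and none of the angles stated can show a canine turning about its long axis

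*Combined protocol and SAP*

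**What the plan says.** The Abstract lists rotation among the features evaluated by CBCT, separately from anchorage loss. The section Measurements used in the CBCT Analysis then describes the angles in two sentences.

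- The first opens by saying that "the canine tipping, torque and rotation were analysed by measuring the angles", and completes this with "the long axis lines for the canines and the three reference planes were measured to detect tipping and torque movements". It is a run-on: it starts by covering rotation and ends by giving the long-axis angles to tipping and torque only.
- The second gives the rule for rotation: "the angle between the horizontal line of the first molar and the sagittal plane to detect canine rotation".

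The section Cone beam Computed Tomography places the landmarks in Table 2 and the reference lines and planes in Table 3, "and measurements (Table 4) were all recorded in their corresponding modules". It adds that "an analysis was created and saved to be used for all pre- & post-retraction CBCT images". Tables 2 to 4 and Figure 4 are not in the text available for review, which is not a fault of the plan.

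On the mechanics, the section Participants, Eligibility Criteria, and Settings describes an indirect anchorage wire placed "in the auxiliary tube of the upper first molar bands and fixed to the mini-screws with flowable composite".

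**The concern.** The tooth named in the measurement is not the tooth named in the outcome. A first-molar line against the sagittal plane can show that the molar has turned. It says nothing about the canine.

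Because a single saved analysis was applied to every image, a wrong line in it would not be an occasional misreading. Every value labelled canine rotation, in both groups and at both time points, would be a molar angle. The molar is also the anchored tooth. If the miniscrew held it still, the stated angle would change little in either group whatever the canine did, and the result could be read as showing no effect of the device on rotation. If the anchorage did not hold, the angle would show molar movement under a canine label. The documents do not say which of these occurred.

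The stakes are limited. Rotation is a secondary CBCT measure, the Statistical Analysis section names no test specifically for it, and the Abstract gives no rotation result.

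**Working it through.** The plan gives no figure for rotation, so there is none to reproduce. The check is whether each stated angle responds when a canine turns about its long axis. Rotation is taken in that sense because the plan names tipping and torque separately.

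**Inputs from the plan.** Three angles use the canine long axis, one against each of three reference planes. One angle uses the first-molar horizontal line against the sagittal plane. That makes 3 + 1 = 4 (per side, if the molar angle is taken on each side, which the text does not state).

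**Formula.** For a line with unit direction *v* and a plane with unit normal *n*, the angle between them is arcsin|*v*·*n*|.

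**Long-axis angles.** Let *a* be the canine long axis and *R* a turn of any size about *a*. Then *Ra* = *a*, so arcsin|*Ra*·*n*| = arcsin|*a*·*n*| for every plane. All three angles are unchanged.

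**Molar angle.** Neither the molar line nor the sagittal plane contains a canine landmark, so *R* does not enter the formula. The angle is unchanged.

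**Numerical illustration.** The tooth directions here are assumptions, not values from the documents: canine axis proportional to (0.15, 0.25, 0.95), molar line proportional to (0.20, 0.97, 0), and planes perpendicular to the three coordinate axes. For comparison, a transverse line on the canine was added, starting parallel to the sagittal plane.

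| Canine turn (°) | Long axis to sagittal / coronal / axial plane (°) | Molar line to sagittal plane (°) | Transverse canine line to sagittal plane (°) |
|---|---|---|---|
| 0 | 8.68 / 14.57 / 72.94 | 11.65 | 0.0 |
| 5 | 8.68 / 14.57 / 72.94 | 11.65 | 4.9 |
| 10 | 8.68 / 14.57 / 72.94 | 11.65 | 9.9 |
| 20 | 8.68 / 14.57 / 72.94 | 11.65 | 19.8 |
| 30 | 8.68 / 14.57 / 72.94 | 11.65 | 29.6 |

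The absolute values depend on the assumed directions, but the lack of change in the four stated angles does not. Only the added canine line, which the section does not mention, follows the turn.

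**The two readings of the text.** If rotation belongs with the molar angle, as the second sentence says, the measure is on the wrong tooth. If it belongs with the long-axis angles, as the opening of the first sentence suggests, the measure cannot change. Neither reading yields canine rotation.

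**The case against.** The strongest reply is that this section is a narrative summary and the governing definitions are in Tables 2 to 4, which cannot be seen here. The text also shows signs of careless drafting: the first sentence is broken and the second has no main verb. The Abstract lists anchorage loss as a CBCT outcome, yet this section gives no measure for it, and a first-molar angle would suit that purpose. Text may have been merged or dropped, or the molar written where the canine was meant. On this view the point is editorial and concerns a secondary measure with no reported result.

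Much of this stands. A slip is quite possible, and nothing here shows that the wrong angle was measured. It is also fair that the miniscrew argument is conditional, and that counting none of four restates the geometry rather than sizing a bias. The invariance further assumes that the drawn long axis is the axis about which the tooth turns. Any departure from this would move the long-axis angles only incidentally and would not make them a measure of rotation.

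It does not remove the need to act. If the tables define a canine line, they contradict this sentence and the sentence must change. If they define the molar line, what is reported as canine rotation must change.

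**Conclusion.** The concern holds for the rule as written. The one angle stated for canine rotation has no canine element, and none of the four stated angles registers a canine turning about its long axis. This rests on rotation meaning a turn about the long axis and on the drawn line representing that axis.

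The size of any error in reported values cannot be given, since the documents contain no canine or molar rotation data. Confidence is moderate because Tables 2 to 4 are unseen. The matter should be put right before any rotation result is reported or interpreted. It does not touch the retraction outcomes from the digital models or the sample size calculation.

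**What to change.** Compare the sentence with Tables 2 to 4 and with the saved analysis, and state which tooth's line was used.

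- **If a canine line was used:** correct the sentence to name that line, and label any first-molar angle as a molar measure. Cost: one sentence.
- **If the molar line was used:** do not report those values as canine rotation. Read a transverse canine line against the sagittal plane on the existing pre- and post-retraction images, and report the change per canine.

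The cost of the second route depends on how many patients were scanned. The imaging section gives a total of 36 images, 18 before and 18 after retraction, so 36 images × 2 canines = 72 angles, or 36 changes. The same section says that "Pre- and post-retraction CBCT images were obtained for each patient". With 32 patients and no drop-outs, that would imply 32 × 2 canines × 2 time points = 128 angles, or 64 changes. Both counts are for one reading each; the documents do not say how many examiners read rotation. No new imaging is needed.

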## **Statistical Analysis**

Data management and statistical analysis were done using Statistical Package

for Social Sciences, Version 21.0 (SPSS Inc., Chicago III) for Windows. Shapiro-Wilk tests of normality were used to test normality of all quantitative variable distributions. Canine retraction in millimetres was presented as mean and standard deviation (SD). Kruskal-Wallis test was used to test the difference in the incremental rate of retraction between the two groups. Independent t-test was used to determine the statistical differences in the total distance travelled.  $P$ -value  $<0.05$  was considered statistically significant. All tests were two-sided. Concordance correlation coefficients (CCCs) were calculated to detect the intra- and inter-examiner reliability of the measurements.

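### The abstract concludes that vibration could not reduce pain during treatment, but pain was scored for one week, the 48-hour result is not given, and non-significance at 16 patients per arm does not show absence of effect

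*Combined protocol and SAP*

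**What the plan says.** The pain paragraph, under Measurements used in the CBCT Analysis, describes 10-cm VAS charts that patients completed during the week after retraction started, "at time intervals (0, 24 hours , 48 hours, 72 hours and 7 days". That makes five scheduled scores per patient.

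The Abstract gives pain P values at "day 0 ( $P=0.721$ ), after 24 hrs. ( $P=0.882$ ), after 72 hrs. ( $P=0.378$ ) and after 7 days", the last being 0.964. There is no 48-hour value and no comment on it. No pain difference or confidence interval is given. The conclusion reads "Pain level couldn't be reduced by vibrational force" and continues "with an AcceleDent device during orthodontic treatment".

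The Statistical Analysis section names two between-group tests. One is a Kruskal-Wallis test for the incremental rate. The other is stated as "Independent t-test was used to determine the statistical differences in the total distance travelled". Neither concerns pain, and the section contains no repeated-measures or summary-measure analysis. The Sample Size Calculation counts canines at d = 0.8 and says nothing about pain.

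On numbers, the Abstract states "Thirty-two patients requiring extraction of upper first premolars and canine retraction were randomly allocated with a 1:1 ratio" and "No patients were dropped-out during this study".

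**The concern.** Pain is listed in the Introduction among the side effects considered, yet it receives its own sentence in the Abstract's conclusion, and that sentence is absolute. Three features undermine it.

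- One of the five scheduled times is not accounted for in the only results supplied.
- The evidence is a set of separate P values above 0.05, with no estimate or interval to show which effects remain plausible.
- The wording covers orthodontic treatment in general, while the measurement covers the first week of retraction.

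A clinician could take the sentence as evidence that the device has no pain benefit. The data described could not show that.

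**Working it through.** **1. The plan's own figure.** Inputs from Sample Size Calculation: d = 0.8, 80% power, 5% significance. Statistical Analysis adds that tests are two-sided. The exact two-sample t calculation gives 25.52 per group, rounded up to 26, so 2 × 26 = 52, with power 80.7%. The stated 52 canines is reproduced. The increase to 64 canines corresponds to two per patient in 32 patients.

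**2. The unit for pain.** The VAS gives one score per patient per time. With 32 patients, 1:1 allocation and no dropouts, that is 16 per arm (assuming an exact split and charts from everyone), not 32 canines per arm.

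**3. Power at a single time, 16 per arm, two-sided 5%, t-test.**

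| True difference (SD units) | Power |
|---|---|
| 0.3 | 13% |
| 0.5 | 28% |
| 0.8 | 59% |

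The difference detectable with 80% power is d = 1.02.

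**4. What the reported P values leave open.** The pain test is not named, so a t-test on 30 degrees of freedom is an assumption. In SD units the standard error is √(2/16) = 0.354, and the 95% half-width is 2.042 × 0.354 = 0.722. The observed difference is |t| × 0.354, with |t| taken from the P value. The direction is not reported, so both limits are shown.

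| Time | P | Observed difference | Limit in the observed direction | Limit in the opposite direction |
|---|---|---|---|---|
| Day 0 | 0.721 | 0.127 | 0.85 | 0.59 |
| 24 h | 0.882 | 0.053 | 0.77 | 0.67 |
| 48 h | not given | – | – | – |
| 72 h | 0.378 | 0.316 | 1.04 | 0.41 |
| 7 days | 0.964 | 0.016 | 0.74 | 0.71 |

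The largest differences not excluded are 0.74 to 1.04 SD. Even if every observed difference went against the device, a benefit of 0.41 to 0.71 SD would remain possible.

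**5. What a week-level estimate would offer.** The mean of k equally correlated scores has its SD multiplied by √((1 + (k − 1)ρ)/k). The documents give no ρ, so 0.3 to 0.9 is assumed, along with an effect that is equal at the times averaged. For the four times from 24 hours to 7 days (k = 4):

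| ρ | SD multiplier | Detectable d (1.024 × multiplier) | Power at d = 0.8 |
|---|---|---|---|
| 0.3 | 0.689 | 0.71 | 89% |
| 0.5 | 0.791 | 0.81 | 79% |
| 0.7 | 0.880 | 0.90 | 70% |
| 0.9 | 0.962 | 0.98 | 62% |

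The gain over a single time (1.02 and 59%) is clear at low ρ and slight at 0.9.

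**6. Why time 0 needs care.** Averaging all five scores gives detectable d of 0.68, 0.79 and 0.89 at ρ = 0.3, 0.5 and 0.7 if the effect is also present at time 0. If it is absent there, the average keeps only 4/5 of the effect. The difference needed at the other four times becomes 0.68 × 5/4 = 0.85, 0.79 × 5/4 = 0.99 and 0.89 × 5/4 = 1.12 (unrounded inputs used). At ρ = 0.7 that is worse than a single-time test. The documents do not say whether the time-0 score precedes device use.

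**The case against.** The strongest reply is that this is a side outcome, that separate between-arm tests at each time are valid because each compares independent patients, and that a joint model is a matter of efficiency. That stands: the separate tests are not wrong in themselves.

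Low power also describes one test rather than the set. In simulations with a constant d = 0.8 at all five times and 16 per arm, at least one of five tests reaches P < 0.05 in 94%, 90% and 83% of runs at ρ = 0.3, 0.5 and 0.7. The five-score average does so in 91%, 81% and 70–71%. So four null results say more against a large, sustained effect than one would, though the separate tests gain this through a looser overall error rate. They do not settle a moderate effect, or one confined to a single time such as 48 hours.

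Two stronger readings are tempting, and the documents do not support either.

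- A reader might infer selective reporting from the missing 48-hour value. Only an abstract's results are available, and an abstract may leave out what a full paper reports. What can be said is that the omission is unexplained.
- A reader might infer inflated false-positive risk from several tests at 0.05. The smallest reported P value is 0.378 and the conclusion is null, so there is no positive finding to protect against. Adjustment would only lower power further (33% at d = 0.8 with Bonferroni over five tests).

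It can also be said that canine retraction is orthodontic treatment and that the methods state the one-week window openly. That makes the wording easy to correct. It does not make it accurate.

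**Conclusion.** The point holds in a limited form. The Abstract's pain conclusion is not supported, because it covers treatment generally on the strength of one week of scores and treats non-significance as absence of effect. Each comparison has 59% power at d = 0.8 and 28% at d = 0.5, and differences of up to 0.74 to 1.04 SD are not excluded at the four reported times. The 48-hour result is unaccounted for in what was supplied.

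These figures rest on 16 analysed patients per arm and on t-tests, neither of which is stated for pain. The size of any gain from a joint analysis also rests on an assumed within-patient correlation and a roughly constant effect. The finding concerns a secondary outcome and leaves the canine-retraction result untouched, but it should be corrected because the sentence stands in the conclusion.

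**What to change.** - Name the pain analysis in the Statistical Analysis section, and report the arm difference with a 95% CI at every scheduled time, including 48 hours. If the 48-hour scores are unusable, say why.
- Estimate one week-level arm difference over 24 hours to 7 days, with a 95% CI, from a single repeated-measures model (arm, time as a category, arm by time, patient as random effect) or from the area under the curve.
- State when the time-0 score was taken relative to first device use. Enter it as a covariate if it came before, and as a further outcome time if it did not.
- Restate the conclusion as no difference in pain detected in the first week after the start of canine retraction, with the interval beside it.

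The cost is one model on data already collected and a few changed sentences. The downside is that a week average can miss an effect confined to one or two times, which is why the time-specific differences should be shown beside it. The gain in precision is small if a patient's scores are highly correlated.
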